14.2 Adverse Event Details

AEs may be either spontaneously reported or elicited during questioning and examination of a subject. All AEs must be recorded on the AE eCRF. If known, the investigator should report the diagnosis of the underlying illness or disorder, rather than its individual symptoms. Subjects experiencing AEs that cause interruption or discontinuation of IP or those experiencing AEs that are present at the end of their participation in the study should receive follow-up as appropriate. AEs should be followed to resolution or stabilization (if possible) and, if they become serious, reported as serious adverse events (SAEs, see [Section 14.3](#)). If possible, the outcome of any AEs that caused permanent discontinuation or that were present at the end of the study, especially those considered by the investigator to be related to the IP, should be reported.

Information on the medical condition of subjects should begin following the subject's written informed consent to participate in the study and a medical history should be taken at screening. During any wash out and screening periods, any changes in the health of subjects should be recorded as changes in medical history unless an event occurred as a result of a study-related procedure and is unanticipated; in such cases, the event should be recorded as an AE and reported to the Institutional Review Board (IRB) as an "unanticipated problem" in accordance with local procedures. Other changes in subject health information becomes AE data when the subject begins dosing with the IP; therefore AE data should be collected from the date of the first dose of IP until the date of the final study visit. These data are considered treatment-emergent AEs.

The investigator will instruct the subject to report any AEs that may occur during the study. At each visit, the investigator should ask the subject, in non-directive fashion, about any change in the subject's overall health status since the previous visit.

The severity of each AE, as judged by the investigator, will be recorded on the appropriate AE eCRF and will be graded according to the following scale:

Mild: The AE is usually transient and may require only minimal treatment or therapeutic intervention. The event does not generally interfere with usual activities of daily living.

Moderate: The AE is usually alleviated with additional specific therapeutic intervention. The event interferes with usual activities of daily living, causing discomfort, but poses no significant or permanent risk of harm to the research participant.

Severe: The AE interrupts usual activities of daily living or significantly affects clinical status, or may require intensive therapeutic intervention.

The investigator must determine the relationship of the AE to the IP according to the following categories:

Definitely Related: An event that follows a reasonable temporal sequence from administration of the IP; that follows a known or expected response pattern to the IP; and that is confirmed by improvement on stopping or reducing the dosage, and reappearance of the event on repeated exposure (re-challenge).

Probably Related: An event that follows a reasonable temporal sequence from administration of the IP; that follows a known or expected response pattern to the IP; and that is confirmed by improvement on stopping or reducing the dosage of the IP; and that is unlikely to have been caused by concurrent/underlying illness or other drugs, procedures, or other causes.

Possibly Related: An event that follows a reasonable temporal sequence from administration of the IP; that follows a known or expected response pattern to the IP; but may have been caused by concurrent/underlying illness, other drug, procedure, or other causes.

Unlikely Related: An event that does not follow a reasonable temporal sequence from administration of the IP; that does not follow a known or expected response pattern to the IP, or most likely was caused by concurrent/underlying illness, other drug, procedure, or other causes, because of their known effects.

Not Related: An event almost certainly caused by concurrent/underlying illness, other drug, procedure, or other causes.

The investigator should categorize the outcome of the AE according to the following categories:

Fatal: Termination of life as a result of an AE.

Not Recovered/Not Resolved: AE has not improved or the subject has not recuperated.

Recovered/Resolved: AE has improved or the subject has recuperated.

Recovered/Resolved with Sequelae: Subject recuperated but retained the pathological conditions resulting from the prior disease or injury.

Recovering/Resolving: AE is improving or the subject is recuperating.

Unknown: Not known, not observed, not recorded or subject refused.

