14.4 Laboratory Test Abnormalities

Any laboratory test results that are outside of normal ranges will be reviewed using the CTCAE version 5.0 classification and by the investigator for clinical significance. Post-baseline, any CTCAE Grade 2 findings or new or worsening clinically significant laboratory test results that meet the criteria for an AE (see [Section 14.1](#)) or SAE (see [Section 14.3](#)) must be recorded on the AE eCRF, in addition to being recorded on the appropriate laboratory test results eCRF and the original laboratory report, as applicable. In these cases, TI will typically require additional information about the clinically significant abnormality, including information regarding relationship to IP, any action taken, and outcome. Clinically significant laboratory abnormalities that qualify as SAEs must be reported to the Sponsor and IRB as per [Section 14.3](#).

Any clinically significant laboratory test result that meets the criteria for an AE (see [Section 14.1](#)) or SAE (see [Section 14.3](#)) must be recorded on the AE eCRF, in addition to being recorded on the appropriate laboratory test results eCRF and the original laboratory report, as applicable. In these cases, TI will typically require additional information about the clinically significant abnormality, including information regarding relationship to IP, any action taken, and outcome. Clinically significant laboratory abnormalities that qualify as SAEs must be reported to the Sponsor and IRB as per [Section 14.3](#).

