All AEs reported during the study will be listed, documenting course, severity, investigator assessment of the relationship to the IP, and outcome. Verbatim terms will be coded to preferred terms (PTs) and system organ class (SOC) using the Medical Dictionary for Regulatory Activities (MedDRA) mapping system (version 26.0). The PTs and SOC will then be tabulated.

All reported AEs will be summarized by the number of subjects reporting AEs, SOC, PT, severity, and relationship to IP by treatment group. For all AE summaries, if a subject has more than one

AE within a PT, the subject is counted once in that PT. If a subject has more than one AE within a SOC, the subject is similarly counted once in that SOC.

The number and percentage of unique subjects reporting each treatment emergent AE (TEAE, events with an onset on or after the first treatment) will be summarized by SOC and PT. The number and percent of unique subjects reporting each TEAE will also be summarized by SOC, PT, and maximum severity (mild, moderate, severe) and closest relationship to IP (not related, unlikely, possibly, probably, definitely).

Serious AEs, if any, will be summarized by SOC, PT, and treatment group.

8.9.7 *Concomitant Medications and Concurrent Therapies/Procedures*

A subject listing of the concomitant medications will be provided. Concomitant medications will be coded using the current version of World Health Organization (WHO) Drug Global Dictionary (version 01March2023). A separate listing of concurrent procedures and therapies will also be provided as applicable.

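### A symptom-free laboratory AE cannot be graded Moderate on the Protocol 14.2 scale, the scale is not tied to the CTCAE review in 14.4, and no specified table shows laboratory grade by arm

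*Protocol*

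**What the plan says.** Protocol 14.2 applies one scale to all AEs: "The severity of each AE, as judged by the investigator, will be recorded on the appropriate AE eCRF". Section 14.1 counts an abnormal laboratory finding among the signs that can be an AE, and no separate scale exists for laboratory AEs. The three categories are:

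- **Mild:** "The AE is usually transient and may require only minimal treatment or therapeutic intervention", and "The event does not generally interfere with usual activities of daily living".
- **Moderate:** "The AE is usually alleviated with additional specific therapeutic intervention", and "The event interferes with usual activities of daily living, causing discomfort, but poses no significant or permanent risk of harm".
- **Severe:** "The AE interrupts usual activities of daily living or significantly affects clinical status, or may require intensive therapeutic intervention".

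Protocol 14.4 adds a second system for laboratory data: "Any laboratory test results that are outside of normal ranges will be reviewed using the CTCAE version 5.0 classification", alongside the investigator's own view of clinical significance. It names post-baseline Grade 2 findings among the results to be entered on the AE form. It does not say how a CTCAE grade translates into Mild, Moderate or Severe.

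SAP 8.9.6 summarises treatment-emergent AEs by "maximum severity (mild, moderate, severe") and by relationship to product. SAP 8.9.5 commits to listings of all laboratory data and to shift tables by analyte and out-of-range flag. The SAP's laboratory and AE sections (7.6, 8.9.5, 8.9.6) do not mention CTCAE.

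**The concern.** The product is a thyroid-receptor agonist. The protocol's Background says that systemic toxicity concerns have kept this class out of AGA trials. Thyroid function, lipids, liver enzymes and cardiac biomarkers are therefore measured at four post-baseline visits, and changes in them may cause no symptoms. AE severity is part of the first safety endpoint, and 14.1 gives recognition of dose-related toxicity as one purpose of AE reporting.

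A severity scale that leans on daily activities and discomfort suits clinical complaints. It suits a raised enzyme or a suppressed hormone poorly. If the middle category is closed to such findings and the laboratory tables do not separate small from large departures, a rise in grade with dose is harder to see than it need be.

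**Working it through.** The documents give no figure to reproduce here. The check sets the sections side by side.

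**Step 1. Place a symptom-free laboratory AE on the 14.2 scale.**

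| Category | Criteria in 14.2 | Can a symptom-free laboratory AE meet it? |
|---|---|---|
| Mild | Usually transient, minimal treatment; no general interference with activities | Yes on activities. Awkward if the abnormality persists or needs specific treatment |
| Moderate | Specific intervention usually helps; interference with activities and discomfort, with no alternative offered | No |
| Severe | Activities interrupted, or clinical status significantly affected, or intensive intervention possibly needed | Not by the first limb. Possible by the second or third, on the investigator's judgement |

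Two of the three categories remain. The event is Mild unless the investigator uses the second or third limb of Severe.

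**Step 2. Bring in the CTCAE grade from 14.4.** The grade appears in none of the 14.2 definitions, and 14.4 assigns no severity from it. Two consequences follow:

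- A symptom-free Grade 2 laboratory AE cannot be Moderate. It would usually be entered as Mild, in the same row as a Grade 1 event.
- A symptom-free AE of a higher grade is Mild or Severe according to how each of about 12 sites reads the clinical-status limb. No rule makes that reading consistent.

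**Step 3. Look for the grade elsewhere in the SAP.** The three safety sections are not written alike:

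- 8.9.2 (vital signs): observed values and change from Baseline by arm.
- 8.9.4 (ECG): observed values and change from Baseline by arm, plus a shift table.
- 8.9.5 (laboratory): listings, and shift tables by out-of-range flag.

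An out-of-range flag puts a marginal and a marked elevation in the same cell. No specified table counts subjects by grade and arm.

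**Step 4. Size.** Inputs: about 72 subjects, 24 per arm (Protocol synopsis); laboratory tests at Weeks 4, 8, 12 and 16; the analyte list in Protocol 12.1.

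- Blood analytes: 18 chemistry + 2 lipid + 3 thyroid + 14 hematology + 3 cardiac = 40.
- Scheduled post-baseline blood results: 40 × 4 × 72 = 11,520, or 40 × 4 × 24 = 3,840 per arm.
- Weight of one subject in an arm's severity row: 1/24 = 4.2%; of two subjects: 2/24 = 8.3%.

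The 11,520 is a count of scheduled results with full attendance. It does not count AEs or misgraded AEs. The documents give no rate from which the number of laboratory AEs could be estimated.

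**The case against.** A reader might infer that every symptom-free laboratory AE is Mild whatever its CTCAE grade, and so that the severity table is bound to understate laboratory toxicity. The text does not support this. Severe has three alternatives joined by or, and two of them need no symptoms. Severity is also the investigator's judgement, and Mild has wording of its own on duration and treatment that a persistent or treated abnormality does not fit well. Understatement is likely for findings between Mild and Severe, but it is not demonstrated.

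A reader might also infer that the size of laboratory changes will be invisible by arm. That goes too far. Change from Baseline in laboratory tests is a declared safety endpoint (Protocol 17.3.2, SAP 3.3). The general rule in SAP 8.2 provides descriptive statistics and/or frequency tables for safety variables, including means and maxima by treatment group for continuous variables. Those summaries may well be produced. However, 8.9.5 does not commit to them as 8.9.2 and 8.9.4 do for their data, and means and maxima do not say how many subjects reached each grade.

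Three further objections have force:

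- The sentence in 14.4 naming Grade 2 findings ends with a qualifier about meeting the AE criteria, which can be read as covering both items in it. Protocol 12.1 and SAP 7.6 tie laboratory AEs to clinical significance. It is therefore not settled that a result can enter on grade alone. The gap in Moderate does not depend on this, because a clinically significant finding can also be free of symptoms.
- Section 14.4 says results are reviewed using CTCAE. It does not say that a grade is recorded for each one.
- The documents do not show that CTCAE grades every listed analyte.

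The last two bear on how the fix is written and what it costs. They do not remove the gap.

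**Conclusion.** The point holds as a gap in the grading rule and in the specified tables. The 14.2 scale has no Moderate category open to a symptom-free laboratory AE, 14.2 and 14.4 apply two unreconciled systems to the same event, and SAP 8.9.5 specifies no output by grade. The conclusion takes the definition of Moderate as written, with interference and discomfort both required.

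The effect on the final tables cannot be quantified from the documents. It depends on how many laboratory AEs arise and on how investigators use the Severe limbs. With 24 subjects per arm, one or two subjects in a different row shift a percentage by 4.2 or 8.3 points, which is enough to blur a dose pattern in a descriptive safety summary. The change is worth making because it is cheap and affects reporting only.

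**What to change.** **Protocol 14.2 and 14.4, and SAP 8.9.6.** State that for an AE based on a laboratory result, where CTCAE v5.0 defines a grade for the analyte, severity is that grade (Grade 1 mild, Grade 2 moderate, Grade 3 or higher severe), or the 14.2 category if higher. For analytes that CTCAE does not grade, the 14.2 category alone applies. This mapping is a proposal; the documents contain none.

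**SAP 8.9.5.** Add a table of worst post-baseline CTCAE grade by analyte and arm, derived from the laboratory values so that it does not depend on a grade having been recorded at site. For analytes without a CTCAE grade, add observed and change-from-baseline summaries by arm and visit, in the form already used in 8.9.2 and 8.9.4. Which analytes these are must be checked, in particular TSH, Total T3, Free T4 and the three cardiac biomarkers.

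**Cost.** A short rule in each document, one or two extra tables, and possibly a data field or programmed derivation for the grade. Some laboratory AEs will move from mild to moderate or severe, so the severity summary will look slightly less favourable.

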The Sponsor is exploring the use of thyromimetics for treating AGA with a suitable topical drug candidate for potential clinical application. The Sponsor has developed TDM-105795 topical solution for the potential treatment of AGA. TDM-105795 is a thyroid hormone receptor-beta agonist being developed as a topical drug to promote hair growth. Preclinical assessment of TDM-105795 indicated that TDM-105795 has poor systemic absorption following topical application and short elimination half-life to avoid unwanted systemic effects. Moreover, an *in vivo* efficacy study in C3H mice suggests that TDM-105795 was able to potently stimulate hair growth in telogen follicles in a dose-dependent manner when applied topically. This is likely because TDM-105795 is able to induce a premature initiation of anagen in telogen hair follicles when binding to thyroid receptors in hair follicle cells. No overt abnormality was observed associated with the treatment. TDM-105795 therefore has a potential to be a novel, potent, and safe therapy to promote hair growth in AGA.

One first-in-man, single ascending dose pharmacokinetic (PK) study was conducted with TDM-105795 (Study 239-11651-101). In this study, 30 male subjects with moderate to severe AGA were studied; subjects received a single dose of 0.025 mg (N=8), 0.05 mg (N=8), 0.1 mg (N=8), or placebo (N=6) applied to the scalp in the hair loss area (e.g., top of head and temple regions) and had PK blood draws at pre-dose and 0.5, 1, 1.5, 2, 3, 4, 5, 6, 8, 10, 12, 24, and 48 hours after the dose. No measurable plasma drug levels were detected in any samples for any subjects (below the limit of quantification of 5 pg/mL). There were no adverse events (AEs) and no local skin reactions

(LSRs) of erythema, edema, erosion, scaling, pruritus, and burning/stinging for all subjects across all visits. There were no materially clinically significant changes in vital signs, clinical laboratory tests (including thyroid function), and electrocardiograms (ECGs).

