14.1 Adverse Event Definitions

An **adverse event** is any untoward medical occurrence associated with the use of a drug in humans, whether or not considered related.

An AE (also referred to as an adverse experience) can be any unfavorable and unintended sign (e.g., an abnormal laboratory finding), symptom, or disease temporally associated with the use of a drug, without any judgment about causality. An AE can arise from any use of the drug (e.g., off-label use, use in combination with any drug) and from any route of administration, formulation, or dose, including an overdose.

A **suspected adverse reaction** is any AE for which there is a reasonable possibility that the drug caused the event. "Reasonable possibility" means there is evidence to suggest a causal relationship between the drug and the AE.

An **adverse reaction** is any AE caused by a drug. Adverse reactions are a subset of all suspected adverse reactions for which there is reason to conclude that the drug caused the event. A suspected adverse reaction implies a lesser degree of certainty about causality than adverse reaction, which means any AE caused by a drug. For the purposes of prescription drug labeling, the term adverse reaction means an undesirable effect, reasonably associated with the use of a drug that may occur as part of its pharmacological action or may be unpredictable in its occurrence.

An AE or suspected adverse reaction is considered "unexpected" if it is not listed in the IB or is not listed at the specificity or severity that has been observed. For example, under this definition, hepatic necrosis would be unexpected (by virtue of greater severity) if the IB referred only to elevated hepatic enzymes or hepatitis. Similarly, cerebral thromboembolism and cerebral vasculitis would be unexpected (by virtue of greater specificity) if the IB listed only cerebral

vascular accidents. "Unexpected," as used in this definition, also refers to AEs or suspected adverse reactions that are mentioned in the IB as occurring with a class of drugs or as anticipated from the pharmacological properties of the drug, but are not specifically mentioned as occurring with the particular drug under investigation.

Timely and complete reporting of all AEs assists the Sponsor and/or their designee (e.g., Therapeutics, Inc. [TI]) in identifying any untoward medical occurrence, thereby allowing:

- 1) protection of the safety of study subjects;

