Any suspected adverse reactions that are serious and unexpected represent especially important safety information that must be reported more rapidly to Health Authorities; therefore, it is important that the Investigator submit any information requested by the Sponsor or designee (e.g., TI) as soon as it becomes available.

If only limited information is initially available, follow-up reports are required. Should the investigator become aware of an SAE (regardless of its relationship to IP) that occurs within 30 days after stopping the IP, the SAE must be reported in accordance with procedures specified in this protocol. In the event of death, if an autopsy is performed, a copy of the report should be sent to TI, if available.

As required, the Sponsor or designee (e.g., TI) will notify participating investigators of all suspected adverse reactions that are serious and unexpected. This notification will be in the form of an IND safety report of potential serious risks as soon as possible but no later than 15 calendar days after the Sponsor determines that the information is “reportable” according to the criteria listed in 21 CFR Section 312.32. These are:

- i) Serious and unexpected suspected adverse reactions;
- ii) Findings from other studies including epidemiological studies, pooled analyses, or other clinical studies that suggest a significant risk in humans exposed to the IP;
- iii) Findings from animal or in vitro tests that suggest a significant risk to humans exposed to the IP, or reports of significant organ toxicity at or near the expected human exposure; and
- iv) Clinically important increases in the rate of occurrence of serious suspected adverse reactions.

Upon receiving such notices, the investigator must review and retain the notice with the IB and promptly submit a copy of this information to the responsible IRB according to local regulations. The investigator and IRB will determine if the informed consent requires revision. The investigator should also comply with the IRB procedures for reporting any other safety information. Where required, submission of safety updates by the investigator to Health Authorities should be handled according to local regulations.

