17.3.2 Safety Endpoints

1. Incidence (severity and causality) of any local and systemic AEs.
2. Number of subjects with presence (and severity) of the following LSRs: erythema, edema, erosion, scaling, pruritus, and burning/stinging at each time point.
3. Changes from Baseline in vital signs at each time point.
4. Changes from Baseline in clinical laboratory tests (chemistry [including lipid panel and thyroid function], hematology, and urinalysis, and cardiac biomarkers) at Week 4, Week 8, Week 12, and Week 16.
5. Changes from Baseline in ECG parameters and overall ECG interpretation at Week 4, Week 8, Week 12, and Week 16.

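### The AE causality scale makes a known or expected response pattern a condition of every related grade, so a reaction that is neither known nor foreseeable cannot be graded even Possibly Related.

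*Protocol*

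**What the plan says.** Protocol 14.2 makes use of the five grades mandatory. The three upper ones share one element:

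- Definitely Related: an event "that follows a known or expected response pattern to the IP; and that is confirmed by improvement on stopping or reducing the dosage, and reappearance" on re-exposure.
- Probably Related: the event must follow a "known or expected response pattern to the IP; and that is confirmed by improvement on stopping or reducing the dosage of the IP", with other causes unlikely.
- Possibly Related: an event "that follows a known or expected response pattern to the IP; but may have been caused by concurrent/underlying illness" or another listed cause.

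Lack of such a pattern appears only under Unlikely Related, beside poor timing and a more likely other cause. Not Related needs an almost certain other cause.

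Protocol 14.1 defines a suspected adverse reaction by a reasonable possibility of causation, meaning that "there is evidence to suggest a causal relationship between the drug and the AE". It treats unexpectedness as a separate property, judged against the Investigator's Brochure. Protocol 14.3 adds: "Any suspected adverse reactions that are serious and unexpected represent especially important safety information".

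The grade is used in safety endpoint 1 (Protocol 17.3.2), "Incidence (severity and causality) of any local and systemic AEs", and in SAP 8.9.6, which tabulates TEAEs by "closest relationship to IP (not related, unlikely, possibly, probably, definitely". Protocol 13.2 also refers to 14.2 for the meaning of an IP-related AE in its follow-up rule after withdrawal, but 14.2 does not say which grades are meant.

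**The concern.** A causality scale in early development should be able to register a reaction that nobody foresaw. Here, fitting what is already known or expected is a precondition of being called related, so the relationship table is least able to record the events that would be new information.

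The point has more weight for this product because the human experience described in the Protocol Background is short. Of the single-dose study it says "There were no adverse events (AEs) and no local skin reactions". The other study enrolled 32 subjects, including placebo, for 4 weeks and is described as well tolerated. Treatment here lasts 16 weeks. In addition, Protocol 10.4.4 keeps the six listed local skin reactions out of the AE data unless they need medical intervention, while any reaction to the product not on that list is recorded as an AE. Unlisted reactions are thus routed to the scale that may be unable to grade them as related.

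**Working it through.** The documents give no figure on this point, so the check is mainly one of logic. Take an event with reasonable timing, no evident other cause, and a pattern that is neither known nor expected, and test it against each grade in 14.2.

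| Grade | Pattern condition | Does the event fit? |
|---|---|---|
| Definitely | Required, with timing, improvement on stopping or reducing, and recurrence on re-exposure | No |
| Probably | Required, with timing, improvement on stopping or reducing, and other causes unlikely | No |
| Possibly | Required, with timing | No |
| Unlikely | Absence of a pattern is listed | Depends on the reading |
| Not Related | None; needs an almost certain other cause | No |

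No alternative or exception relaxes the condition in the top three rows. For Unlikely Related the punctuation allows two readings. If poor timing, no pattern and another likely cause are separate alternatives, the event is Unlikely. If poor timing and no pattern must occur together, the event fits no grade.

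Now compare with 14.1. The same event can be a suspected adverse reaction if the evidence suggests causation, because 14.1 sets no pattern requirement. If it is absent from the Investigator's Brochure it is also unexpected. Protocol 14.1 and 14.3 therefore recognise it as a suspected, unexpected reaction, while 14.2 cannot grade it as related. For a serious event, 14.3 asks separately for a reasonable-possibility assessment, so one event could be a suspected reaction on the SAE report and Unlikely on the AE eCRF. A non-serious event has only the 14.2 scale.

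Size, as illustration only:

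- Planned arm size is 24 (Protocol Synopsis). One subject regraded out of the related rows moves an arm's incidence by 1/24 = 4.2 percentage points.
- Assume, without support in the documents, that 20% of an arm truly has a related AE (0.20 × 24 = 4.8 subjects expected, one such AE each), and that a share f of these is of an unforeseeable type graded to the letter. The incidence shown as possibly or higher is 0.20 × (1 − f).
- f = 25%: 0.20 × 0.75 = 15%. f = 50%: 0.20 × 0.50 = 10%. f = 100%: 0%.

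Through this mechanism the bias is zero or downward. Its amount cannot be derived from the documents.

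**The case against.** The strongest reply is that known or expected is wider than seen before with this product. Protocol 14.1 classes as unexpected even reactions anticipated from the drug class or pharmacology, if they are not specifically listed for this drug. Such a reaction can be unexpected under 14.1 and still follow an expected pattern under 14.2; so can one that is unexpected only because of greater severity or specificity. A reader might infer that any event without precedent has no related grade open to it, or that the suspected-and-unexpected class is empty on this scale. The documents do not support either inference, and this part of the reply stands: the gap covers only reactions that are neither known nor foreseeable. It leaves one residue. Section 14.2 does not say in which sense it uses expected, so two sites could grade the same event differently.

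It also stands that the Investigator's Brochure, to which Protocol 14 refers for known AEs, is not among the documents. How small the known pattern really is therefore cannot be settled here.

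Finally, much of the safety record does not use the scale. All AEs are listed, TEAEs are tabulated by SOC and PT regardless of causality, and laboratory, ECG and local skin reaction summaries are separate. All SAEs are reported whether related or not. Protocol 14.2 also asks that AEs generally be followed to resolution or stabilization where possible, which softens the effect on the 13.2 rule. This limits the consequence to the causality breakdown, mainly of non-serious AEs, but does not remove the conflict between 14.2 and 14.1.

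**Conclusion.** The point holds as an internal conflict with a bounded effect. A reaction with reasonable timing that is neither known nor foreseeable cannot reach Possibly Related under 14.2, although 14.1 would allow it to be a suspected reaction. The possibly, probably and definitely rows of the SAP relationship table will be too low to the extent that two conditions are met: such reactions occur, and investigators apply the wording literally.

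Two stronger conclusions should be avoided. One is that related-AE incidence is understated as a matter of fact; only the direction follows from the text. The other is that these events will be recorded as Not Related; that grade needs an almost certain other cause, and the event may instead fit no grade. The SAP also defines no pooled related category, so the effect is on separate rows of one table.

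The wording is a mandatory rule that feeds a stated safety endpoint, and it is cheap to correct. It should be corrected.

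**What to change.** In Protocol 14.2:

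- Remove the pattern condition from Possibly Related. Define it as a reasonable temporal sequence and a reasonable possibility that the product caused the event, although another cause is also possible.
- Make clear that absence of a known pattern does not by itself place an event in Unlikely Related.
- State that Possibly, Probably and Definitely Related together correspond to the reasonable-possibility standard of 14.1. This also supplies the missing definition of an IP-related AE for 13.2.

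In SAP 8.9.6, add one sentence that uses the same three grades as the related grouping. Carry the changes into the eCRF completion guide.

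The cost is small wording changes and a related-AE count that may be slightly higher.
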